- Anastomotic leakage identified radiologically or clinically
or
- Intraperitoneal (abdominal or pelvic) fluid collection identified radiologically, as per the Centre for Disease Control Criteria for Organ Space infection
or
- Entero-enteric fistula identified radiologically

Secondary outcome measures

- The denominator is the total for patients who had a primary anastomosis:
- Reoperation for anastomotic leak, within 30-days
- The denominator is the total for all patients:
- Reoperation for any cause, within 30-days
- Unplanned admission to critical care, within 30 days
- Readmission within 30 days.
- Post-operative length of hospital stay, up to 30-days
- Mortality within 30-days.
- Rate of ileostomy without anastomosis.
- Rate of defunctioning ileostomy with anastomosis.

Study Design

International prospective audit.

ELIGIBILITY

Hospital inclusion criteria

Any hospital or surgical unit performing elective and/or emergency colorectal surgery. There are no restrictions for hospital/unit size or case volume. Participation in EAGLE 1 is not a pre-requisite.

Participating sites will be expected to recruit all eligible patients within a consecutive 8-week period.

At hospital level, data completeness of 95% will be required to be part of this audit.

Patient inclusion criteria

All adult patients (age 18 years and above) undergoing right colectomy with or without primary anastomosis. Right colectomy is defined as ileocaecal resection or right hemicolectomy (any colonic transection with the distal resection margin proximal to the splenic flexure).

All patients undergoing right colectomy are eligible, including those who do not have an anastomosis and are defunctioned by a proximal stoma.

Procedures for any pathology, via any operative approach (open, laparoscopic, robotic or converted) are eligible.

Elective (surgery on a planned admission), expedited (within 48 hours), and emergency (surgery on an unplanned admission) procedures are eligible.

Patient exclusion criteria

Patients undergoing more than one gastrointestinal anastomosis during the same operation.

In Crohn's disease, additional upstream strictureoplasty or resection/anastomosis to treat disease or strictures at the same operation.

Simultaneous right colectomy and hyperthermic intraperitoneal chemotherapy (HIPEC) and/or cytoreductive surgery.

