All patients, including those who did not have a primary anastomosis, will be followed-up to a maximum of 30-days post-operatively (with Day 0 being the day of surgery) by a review of their inpatient health records, routine clinic visit letters, and reports for post-operative radiological investigations arranged as part of normal patient care. There will be no additional patient contact (telephone or in-person) beyond what is normal clinical practice at each centre. The study is designed efficiently so that existing patient follow-up pathways and health records can be used, with only data that is routinely collected as part of normal clinical care being captured.

Most anastomotic leaks following ileocolic anastomosis occur in the early post-operative period (days 4-14). Although a small number of anastomotic leaks occur beyond day 30, limiting follow-up to 30 days will ensure that the vast majority of leaks are captured.

Statistical analysis plan

This will be conducted on an intention-to-treat basis i.e. all patients recorded in the database during the scheduled 2-month recruitment periods will be included, and those in the second period will be considered exposed to the intervention regardless of whether learning from the intervention was actually implemented. The primary outcome will be 30-day anastomotic leak rate. In the primary analysis, 30-day leak rate will be modelled using mixed effects logistic regression with random cluster (hospital) effects allowing inclusion of baseline risk factors such as co-morbid disease and ASA score and adjustment for a fixed time effect between time periods.

Sample size

Based on feasibility (below), we assume that if each hospital provides data on 10 patients over a 2-month recruitment period (5 per hospital per month) then adequate sample size will be obtained to allow statistical analysis (see below please).

Projected recruitment

Data for 3,208 right colectomies was submitted by 284 centres over a 2 month period to the 2015 ESCP Right Hemicolectomy Audit; an average of 11.3 patients per 2 months. 81% the sites recruited >10 patients over the 2-month period. A mean of 10 patients per centre is required for each 2 month recruitment period.

| Patients per centre (2 months) | Proportion of centres |
|---------------------------------------|------------------------------|
| 1-5 | 19% (n=53) |
| 6-10 | 37% (n=104) |
| 11-15 | 22% (n=63) |
| 16-20 | 14% (n=39) |
| 21-30 | 6% (n=17) |
| 31+ | 3% (n=8) |

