Planned additional analyses

Pre-planned exploratory sub-group analyses of the primary outcome will be performed in the following groups:

- *At cluster (hospital) level:*
- Number of beds (<500 versus ≥500 total hospital beds).
- Right colectomy volume (<10 patients versus ≥10 patients per 2 month period).
- Early adoption (early versus late study entrants).
- Health service expenditure per capita in purchasing parity (top versus middle versus bottom tertile).
- Proportion of operating surgeons in each centre completing the online training modules prior to 'post-implementation' data collection (high [≥80%], intermediate [50-79%], low [<50%]).
- World Bank income group (high versus middle/low-income country).

At patient level:

- Indication for surgery (malignant versus benign, e.g. inflammatory bowel disease).
- Procedure urgency (elective versus expedited/ emergency).
- Age (≤65 years versus >65 years).
- Operative approach (open versus laparoscopic/ robotic).
- Anastomotic technique (stapled versus handsewn anastomosis).
- Primary operating surgeon experience as reported (trainee versus consultant).
- Primary operating surgeon specialism as reported (general versus colorectal surgeon).
- Reverse analysis will also be undertaken to explore what are the characteristics of hospitals with a big change versus no change, and do these differ in respect of cluster characteristics.

STUDY ORGANISATIONAL STRUCTURE

EAGLE 2 Audit Office

The coordinating centre for EAGLE 2 is based at the University of Birmingham in the Birmingham Centre for Observational and Prospective Studies (BiCOPS). Members of this group also represent the European Society of Coloproctology (ESCP) and sit on both the research committee and cohort studies committee of ESCP.

Local teams

We envisage that most hospitals opening for the audit will identify a team of up to 5 members, which may include surgical colleagues, trainee doctors, nurses, medical students, or others involved in the routine clinical care of eligible patients, depending on local circumstances. Members of this group will be responsible for the local conduct of the audit at their site, including helping to identify potential patients and record data onto the EAGLE 2 REDCap database.

Publication policy

The output from this research will be published under a single corporate authorship group: “European Society of Coloproctology (ESCP) collaborating group”.

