APPENDIX 1. EAGLE 2 Case Report Form

| Local Patient Identifier | not uploaded to REDCap | Unique REDCap Identifier | |
|---|---|--------------------------|--|
| Pre-operative data | | | |
| Age (on day of operation) | Years | | |
| Sex | Male / Female | | |
| American Society of Anaesthesiologists (ASA) grade | 1 / 2 / 3/ 4/ 5 | | |
| Previous abdominal surgery | No / Yes | | |
| History of ischemic heart disease or cerebrovascular disease | No / Yes | | |
| History of diabetes mellitus | No / Yes | | |
| Body Mass Index >30 | No / Yes | | |
| Oral anti-coagulants | No / Yes | | |
| Pre-operative total protein level (g/dL) – nearest 0.5 units | | | |
| Pre-operative haemoglobin (g/dL) | | | |
| Procedure indication | Malignancy / Inflammatory bowel disease / Other | | |
| Intra-operative data | | | |
| Bowel preparation | None / Mechanical bowel preparation only / Mechanical bowel preparation with oral antibiotics | | |
| Primary operating surgeon | Consultant colorectal surgeon / Trainee colorectal surgeon / Consultant general surgeon / Trainee general surgeon | | |
| Most senior surgeon in theatre | Consultant colorectal surgeon / Trainee colorectal surgeon / Consultant general surgeon / Trainee general surgeon | | |
| Procedure urgency | Elective (planned) / Expedited (within two weeks of decision to operate) / Emergency (unplanned) | | |
| Operative approach | Open, Laparoscopic (completion, conversion to open), Robotic (completion, conversion to open) | | |
| Operative field contamination | Clean-contaminated / Contaminated / Dirty | | |
| Anastomosis formed | Stapled / Handsewn / No anastomosis (end ileostomy formation) | | |
| If yes: Anastomotic configuration | Side-to-side / end-to-side / end-to-end | | |
| If yes: Is there a defunctioning loop ileostomy | No / Yes | | |

| | |
|---|--|
| If yes: Was the anastomosis tested? | No / Yes -air leak test / Yes - probed with forceps |
| If yes: Did the anastomosis require revision? | No / Yes |
| Intra-operative complications | Blood loss >1L / Operating time >4h / Solid organ or ureteric injury / Vascular injury / Blood transfusion / Hemodynamic instability / Vasopressor requirement (select all that apply) |
| Duration of surgery (minutes) knife-to-skin to completion of skin closure | 1-60 / 61-119/ 120-179/ 180-239/ ≥240 |
| Was an ESCP Safe-anastomosis Checklist completed? | Yes / No |
| Was anastomotic leak risk calculated pre-operatively ? | Yes / No |

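### The exploratory leak analyses cut age at 65 years and hospital volume at 10 patients, although both are available in full; under a steady trend this loses roughly 36–50% of the information

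*Protocol*

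**What the plan says.** Under Planned additional analyses the protocol states: "Pre-planned exploratory sub-group analyses of the primary outcome will be performed in the following groups". The hospital-level list includes "Right colectomy volume (<10 patients versus ≥10 patients per 2 month period" and the patient-level list includes "Age (≤65 years versus >65 years". No reason is given for either cut-point, and no analysis of either measure on its full scale is mentioned.

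Both measures are available in finer form:
- **Age.** The Appendix 1 case report form collects it in years: "Age (on day of operation) | Years".
- **Volume.** It follows from the consecutive series at each site: "Participating sites will be expected to recruit all eligible patients within a consecutive 8-week period".

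Projected recruitment describes the 2015 audit, with "Data for 3,208 right colectomies was submitted by 284 centres over a 2 month period" and "an average of 11.3 patients per 2 months". It also tabulates centres by volume band. The Statistical analysis plan section of the protocol already specifies a mixed logistic model for leak with a random hospital effect and baseline risk factors.

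**The concern.** Splitting a graded measure in two treats everyone on one side as alike. Centres with 9 and 10 patients are set apart, while centres with 10 and with more than 30 are merged; ages 66 and 90 are merged likewise. If leak risk changes gradually with age or volume, the variation within each group is discarded and the comparison becomes less precise.

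These comparisons are thin to begin with: the protocol quotes a leak rate of about 8% and plans on about 10 patients per hospital. A real gradient could be missed, or reported as no difference, partly because of the split.

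**Working it through.** **Approach.** For a weak, steady trend on the logit scale, the share of information kept by a two-group version is approximately r², the squared correlation between the measure and its group indicator. If the full-scale one-degree-of-freedom test had power P, the two-group test has power of about Φ(√r² × (1.96 + z_P) − 1.96). The protocol states no power for these analyses, so P = 80% (z_P = 0.8416, sum 2.8016) is purely illustrative.

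**Inputs from Projected recruitment.** Centres by volume band: 1–5, 53; 6–10, 104; 11–15, 63; 16–20, 39; 21–30, 17; 31 or more, 8. They sum to 284, and 3,208 / 284 = 11.30, which reproduces the stated average. A sentence in the same section puts 81% of sites above 10 patients. The table gives (63 + 39 + 17 + 8) / 284 = 127 / 284 = 44.7%, while 81% is the share with 6 or more (231 / 284). I use the table because it agrees with the stated average.

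**Volume.** Spread centres evenly within bands, weight by patients, take x = log(volume), and set the indicator to 1 for volume of at least 10. With p the share of patients in the upper group and m1, m0 the group means of x, r² = p(1 − p)(m1 − m0)² / Var(x). The top band is open, so its upper end is varied.

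| Top band | Mean volume | p | m1 − m0 | Var(x) | r² | Loss | 80% power becomes |
|---|---|---|---|---|---|---|---|
| 31–35 | 11.30 | 0.756 | 1.000 | 0.326 | 0.567 | 43% | 56% |
| 31–45 | 11.44 | 0.759 | 1.029 | 0.358 | 0.541 | 46% | 54% |
| 31–60 | 11.65 | 0.763 | 1.074 | 0.417 | 0.500 | 50% | 51% |

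For the first row: 0.756 × 0.244 × 1.000² / 0.326 ≈ 0.567, and Φ(0.753 × 2.8016 − 1.96) = Φ(0.149) = 0.56. That row matches the stated average of 11.3. Weighting by centre instead gives r² of about 0.56 in all three cases, a loss of about 44%. On the untransformed scale the loss is larger. In sample-size terms the patient-weighted range is a factor of 1/0.567 = 1.76 to 1/0.500 = 2.00.

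**Age.** The protocol gives no age distribution, so a normal one is assumed. With z = (65 − mean)/SD and p the share above 65, r² = φ(z)² / [p(1 − p)].

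| Assumed mean / SD | z | p | r² | Loss | 80% power becomes |
|---|---|---|---|---|---|
| 65 / 15 | 0.00 | 0.500 | 0.637 | 36% | 61% |
| 68 / 14 | −0.21 | 0.585 | 0.626 | 37% | 60% |
| 60 / 18 | 0.28 | 0.391 | 0.619 | 38% | 60% |

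The result moves little with the assumption; mean 60 with SD 14 gives 39%.

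**What a spline test would recover.** A three-knot restricted cubic spline tested jointly uses two degrees of freedom. At the noncentrality that gives 80% power on one degree of freedom (2.8016² = 7.85), the joint test (critical value 5.99) has about 71% power. The full 80% is recovered only by testing the single linear term.

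**The case against.** **The analyses are exploratory.** They are labelled so, and the audit's stated objective is to measure a leak rate. Rates in two prespecified groups are easy to read and suit that purpose. The primary model does not cut age or volume, so the primary estimate is untouched. A separate statistical analysis plan could add continuous terms, and nothing in the protocol forbids them. All of this stands and limits the point to a cheap improvement.

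**The cut at 10 has some context.** Ten patients per hospital per two months is the protocol's own recruitment planning figure. That is a plausible origin, but it is not given as the reason and is not evidence of a threshold in leak risk.

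**The loss depends on the shape of the relation.** It assumes a steady trend. If leak risk changed in a single step exactly at the cut, the two-group analysis would lose nothing.

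**Misclassified hospitals.** A reader might infer that chance variation in an 8-week count puts about one hospital in six or seven in the wrong volume group. Modelling Poisson counts around a true rate does give about 15–17.5%. But the protocol's wording can be read as the count observed in the period, and on that reading no hospital is in the wrong group. The figure holds only against an unobserved long-run rate that the protocol never names as its target. The same noise would remain in a continuous term: the raw count has r² of only about 0.75–0.77 with the true rate in gamma-Poisson models fitted to the table. The documents do not support calling this an error of the cut.

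**Conclusion.** The point holds as a low-cost improvement to two exploratory analyses. Under a steady logit trend, the volume split loses about 43–50% of the information and the age split about 36–38%. A hypothetical 80% power would become about 51–56% and about 60% respectively.

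The volume figure rests on the 2015 table, even spread within bands, the log scale and a top band ending between 35 and 60. The age figure rests on an assumed mean of 60–68 and SD of 14–18, in the pairs shown. Neither the starting power nor the trend is documented.

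A reader might go further and conclude that the audit will wrongly report no effect of volume or age. The documents do not support that: they give no effect size or power for these analyses, and the loss disappears for a true step at the cut.

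**What to change.** In Planned additional analyses, state that the test and confidence interval for age (in years) and for hospital volume (log of the number of eligible patients in the 8-week period) come from a single linear term for each in the mixed logistic leak model already planned. Show a three-knot restricted cubic spline for each as a check on curvature, not as the basis of the test. Keep the leak rates for the two age groups and the two volume groups as descriptive tables.

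The cost is a few lines of wording and one model term per factor, with no new data or patients. A per-unit odds ratio or a curve is slightly harder to read than two rates; the retained tables cover that.

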Background: Anastomotic leak (Al) is a severe, potentially life-threatening complication following right colectomy. Internationally, anastomotic leak occurs after 8% of right colectomies. Prospective cohort data demonstrate that patient selection, intra-operative factors, and technical variation are risk factors for anastomotic leak. The EAGLE study investigated an educational platform to reduce Al. It showed an absolute reduction in leaks of 20% following implementation and found that in centres where 80% of surgeons undertook the training, the anastomotic leak rate fell by almost 50%. EAGLE 2 is a snapshot audit of centres undertaking the educational intervention to validate the findings from the randomised trial.

Aim: To measure the anastomotic leak rate following right sided large bowel anastomosis in centres where the surgical teams have undertaken the EAGLE platform training.

Design: Prospective audit with clinician derived baseline clinical data and short-term 30-day outcomes for patients undergoing right colectomy and ileocecal resection.

Eligibility: Any hospital or surgical unit performing elective and/or emergency colorectal surgery. Adults (age 18 years and above) undergoing right colectomy or ileocaecal resection for any indication are eligible, including elective, expedited or emergency surgery by open, laparoscopic or robotic approaches.

Primary Outcome measure: 30-day anastomotic leak rate, defined as clinical or radiologically detected anastomotic leak or intra-abdominal or pelvic collection.

Sample size: a consecutive series of cases, collected over an 8 week period, of patients undergoing right sided large bowel anastomosis. The study is open to any centres where the surgical team have undertaken the educational training. These may be centres from EAGLE 1 or new centres that did not take part in EAGLE 1.

BACKGROUND

Clinical problem

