| | Short-term Complications / reinterventions | | | ✓ |

Training platform

The training platform for the audit is the ESCP Safe-anastomosis Online Educational Module. This is an Electronic Learning Management System which houses a five-modular educational platform, freely accessible at <https://eagle-escp.eu.com/>. The modules are:

1. **Decision making**, including a pre-operative risk stratification tool for anastomotic leak
2. **ESCP Safe-anastomosis checklist**, including components and implementation within a theatre team
3. **Preparing for anastomosis**, including anastomotic healing bowel preparation, choice of stapled versus handsewn anastomoses
4. **Stapled anastomosis**, including harmonising technique and checking for technical failure.
5. **Handsewn anastomosis**, including harmonising technique, common variations and checking for technical failure.

It is intended that this educational module should be completed by any providers of colorectal surgical procedures (including consultant/attending surgeons, trainee/resident surgeons, and surgical care practitioners/allied healthcare professionals in surgery) prior to participation in the audit.

Validation of learning platform

The training program has been reviewed by the ESCP Education Committee and revised. It has also been reviewed by the independent Study Steering Committee. More than 2500 surgeons completed the online training during delivery of the EAGLE 1 study.

Data collection and follow-up

Data will be collected in two phases. During the index admission pre-operative and intra-operative data will be collected. Local Principal Investigators will establish pathways in their hospitals to ensure robust data collection; for example, pre-operative data could be collected on the morning prior to surgery, with intra-operative data fields completed in theatre immediately following completion of the procedure. Alternatively, all data could be collected in theatre, or in the post-operative ward.

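### The reverse analysis compares hospitals by change in leak rate, but the stated design gives each hospital one post-training period and names no comparator

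*Protocol*

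**What the plan says.** The last item under Planned additional analyses reads: "Reverse analysis will also be undertaken to explore what are the characteristics of hospitals with a big change versus no change". It does not say what the change is measured from, or how large a change counts as big. The same section defines a subgroup by the proportion of surgeons trained before 'post-implementation' data collection.

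The design sections describe something simpler:
- The synopsis defines the sample as "a consecutive series of cases, collected over an 8 week period".
- Hospital inclusion criteria: "Participating sites will be expected to recruit all eligible patients within a consecutive 8-week period", and "Participation in EAGLE 1 is not a pre-requisite".
- Study Design is, in full, "International prospective audit".
- The Training platform section intends the modules to be completed "prior to participation in the audit".

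The Statistical analysis plan section presumes otherwise: "those in the second period will be considered exposed to the intervention regardless of whether learning from the intervention was actually implemented". It also adjusts for a fixed effect of time period. Projected recruitment adds: "A mean of 10 patients per centre is required for each 2 month recruitment period".

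**The concern.** A change needs two measurements. With one 8-week series per site, taken after training, there is only one. A new centre has no earlier data at all. A former EAGLE 1 centre could have a change only through data that the protocol never says it will obtain or link.

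Even if such data were brought in, hospitals would be grouped on a difference between two very small samples. At roughly 10 patients and a leak rate near 8%, fewer than one leak is expected per hospital per period, so a single leak moves the hospital's rate by 10 points. At stake is an analysis that either cannot be run or, for the subset where it can, has little power to find real predictors of response and may give some false weight to centre volume.

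**Working it through.** **1. Is change observable?** The places set side by side:

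| Place in protocol | What it implies |
|---|---|
| Synopsis, sample size | one 8-week series |
| Hospital inclusion criteria | one consecutive 8-week period per site; EAGLE 1 participation not needed |
| Training platform | training intended before the audit, so no untrained period is recorded |
| Data collection and follow-up | two phases, but these are index-admission data and 30-day follow-up on the same patients |
| Statistical analysis plan | a second, exposed period and a time effect |
| Planned additional analyses | change per hospital; 'post-implementation' data |

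The first four rows give no before-and-after contrast. The last two need one. The document names no historical data source that would supply it.

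**2. Inputs for the conditional check**
- Leak rate 8.1% (Existing international data).
- Reduction 20% (same section), read as relative: 0.081 × 0.80 = 0.0648, a true change of 1.62 points. The synopsis calls the 20% absolute, which is not possible from 8%, so the relative reading is an assumption.
- Patients per centre: the protocol's figure reproduces, 3,208 / 284 = 11.3 per 2 months, and the target is 10. Using 10 for an EAGLE 1 comparator period is an assumption, so a range of 10 to 31 is shown.

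**3. Standard deviation of one hospital's observed change**

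SD = √{[p₁(1−p₁) + p₂(1−p₂)] / n}, with p₁ = 0.081 and p₂ = 0.0648. The bracket is 0.0744 + 0.0606 = 0.1350.

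| n per period | SD of change | True change |
|---|---|---|
| 10 | √0.01350 = 11.6 points | 1.6 points |
| 20 | 8.2 points | 1.6 points |
| 31 | √0.004356 = 6.6 points | 1.6 points |

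**4. What a raw classification would show at n = 10.** Suppose every hospital has exactly the same 20% relative reduction. Exact binomial probabilities for the difference in leak counts are:
- fall of at least 10 points: 36.4%
- no change: 37.2%
- rise of at least 10 points: 26.4%

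At 8.1%, 0.919¹⁰ = 43% of hospitals would record no leak in the first period and so could not show a fall.

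**5. How much of the observed variation could be real?** Reliability = τ² / (τ² + SD²), where τ is the true between-hospital SD of change. The protocol does not give τ; 1 to 5 points is assumed.
- n = 10: 0.0001 / 0.0136 = 0.7% to 0.0025 / 0.0160 = 16%
- n = 20: 1.5% to 27%
- n = 31: 0.0001 / 0.00446 = 2.2% to 0.0025 / 0.00686 = 36%

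**6. Does the noise create false predictors?** I simulated 284 centres at about the midpoints of the size bands under Projected recruitment, all with the identical 20% relative reduction. Big was taken as a fall of at least 10 points and no change as within 5 points; both cut-offs are assumptions. A characteristic unrelated to size was significant at the 5% level in about 5% of runs. Volume (10 or more versus fewer) was significant in about 8 to 9%.

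**The case against.** The strongest reply has four parts.

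First, the two-period wording in the Statistical analysis plan section is the root of the problem, and the reverse analysis only follows from it. This stands. A reader might infer that the single-period design is settled and the reverse analysis is a lone slip. The documents do not support that: they contradict themselves, and the passages must be reconciled.

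Second, the noise argument addresses a historical comparison that the protocol does not plan, using a comparator size it does not give. This also stands, so those figures are conditional. A fixed 10 is also too simple, since the protocol's table puts 63 + 39 + 17 + 8 = 127 of 284 centres above 10.

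Third, a reader might infer that the analysis would report features of responding hospitals even if all hospitals responded alike. That is too strong. Noise unrelated to a characteristic mainly costs power. The false-positive rate stayed near 5% for such a characteristic and rose only modestly for volume.

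Fourth, the classification method could be left to a separate analysis plan, and a model-based one is not excluded. True of the method and the cut-off, but no analysis plan can estimate change from a single period. The analysis is also labelled exploratory and the primary objective does not depend on it. That lowers the severity without making the quantity estimable.

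**Conclusion.** The point holds in two parts of different strength.

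Unconditionally, the reverse analysis cannot be run on the design that the synopsis, eligibility and training sections describe, and the analysis text that presumes a second period contradicts that design.

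Conditionally, if an earlier period were borrowed for former EAGLE 1 centres, raw observed change would sort hospitals mostly by chance. With 10 patients per period the SD is about 11.6 points against a true change of 1.6, and at most about 16% of the variance is real for a true spread of up to 5 points. With 31 patients the SD is 6.6 points. This rests on the assumed comparator size, the relative reading of the 20% and the assumed spread. Calling the change pure noise would go further than the documents allow, because they give no between-hospital spread.

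The consequence is low power to find real predictors and a modest artefact for volume-related characteristics, about 8 to 9% instead of 5%. Severity is low to moderate.

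**What to change.** Reconcile the Statistical analysis plan section with the design sections, so that the protocol states one set of data-collection periods. Under the single-period design:
- Delete the reverse analysis and the 'post-implementation' wording.
- Enter hospital characteristics, including the proportion of surgeons trained, as hospital-level covariates in the mixed logistic model with random hospital effects that is already planned, with the EAGLE 2 leak rate as outcome.
- Report the between-hospital variance.
- Do not classify hospitals by observed change.

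This keeps the useful question, namely which hospital features go with lower leak rates, and builds on the hospital-level subgroups already listed. The cost is protocol wording and minor analysis work; no new data are needed.
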